### 7.1.2 Remote Visits

Some of the non-drug psychotherapy sessions and online evaluations may be permitted remotely, via tele-assessment (online video meetings), rather than at the study site. Remote visits if deemed appropriate may be permitted based on prior experience or in the context of local regulation due to a pandemic. There may be benefits to remote visits, such as convenience and reduced risk of COVID-19 transmission. There may be risks, including potential breach of security and technological difficulties or interruptions.

# 7.1.3 Interruptions and Arrangements Due to COVID-19 Pandemic or Any Other Unforeseen Emergency at Clinic Locations

This clinical trial may be impacted by the Coronavirus Disease 2019 (COVID-19) global pandemic. Special arrangements may be required for study continuation and participant and study site staff safety due to this emergency or any other unforeseen emergency in the future. The following accommodations in the protocol will be allowed, captured, and noted in the Clinical Study Report as COVID-19 deviations when applicable:

• Integrative Sessions may be conducted by tele-medicine

- Delaying the start of medication tapering after enrollment and the subsequent Treatment Period per Section 11.1 Tapering Instructions
- Delaying Experimental Sessions and associated Integrative Sessions
- Delaying Independent Rater assessments for participants who cannot complete them remotely off-site
- Use of prohibited medications and/or cannabis or initiation of new therapy for participants with significant study delays, which will be reviewed by the study team before each Experimental Session and re-tapered prior to resuming treatment per Section 11.0 Concomitant Medications.

For any participant with COVID-19 related illness, continued trial participation after full recovery of the disease may be appropriate after discussion between the site physicians and Medical Monitors on a case-by-case basis.

## 7.1.4 Independent Rater Screening

If participants meet initial eligibility during Screening, an IR will continue the eligibility assessment via tele-assessment after reviewing the results of the LEC-5 and CIPD-SR. The IR interview will be recorded to assess reliability of ratings. If possible, the potential participant should be present at the study site during this assessment, in case the therapy team is needed for support. If a participant reports suicidal ideation during this assessment, the IR will contact the therapy team after the call and present any concerns. The therapy team will follow-up with the participant to ensure safety, provide support, recommend treatment, or schedule a visit to the study site.

- Using the results of the CIPD-SR to guide the interview, the IR will perform the CIPD to assess personality disorders. Only appropriate modules will be completed.
- The IR will also ask relevant questions from the DDIS to identify dissociative disorders and administer the Since Last Visit C-SSRS to determine suicidal risk.
- The IR will complete MINI interview to assess Axis I psychiatric disorders.

The results from the MINI, CIPD, DDIS, and C-SSRS will be provided to the therapy team at the site to review along with all other Screening information to determine eligibility. Items assessed by the IR at this visit will be confirmed in the Preparatory Period by clinical observation, but the measures will not be repeated. If site staff deem the participant eligible, schedule Enrollment (Visit 0).

If the results of the any measure or interview indicate a diagnosis is present, the investigator is not permitted to use their clinical judgment to question the diagnosis. However, if a diagnosis is not present or uncertain according to any measure or interview, but the investigator believes the participant presents with a particular disorder, they may diagnose and deem the participant ineligible for the trial.

#### 7.1.5 Enrollment

In advance of Visit 0, the site team will review all notes from Screening visits, medical assessments, IR assessments, notes, discussions, medical records, and measures against eligibility criteria. If the participant is eligible, medication tapering and concomitant medications dose adjustments will be discussed, if applicable. The site physician will consult the prescribing physician to initiate medication tapering for participants. For all details on concomitant

medications, tapering, allowed, and prohibited medications refer to Section 11.0 Concomitant Medications.

At study onset at each site, if a potential participant is eligible, the study team will contact the Medical Monitor to discuss the medical history and screening data available for review to confirm the potential participant is eligible for enrollment.

If a participant is confirmed as eligible for enrollment, the participant will be notified of enrollment at Visit 0 in-person, via tele-assessment, or by telephone.

Medical history and medication information will be reviewed for completeness. A medication tapering plan will be discussed with the participant, if applicable. If agreeable, the participant will be enrolled in the study. Once enrolled, AE collection requirements begin (refer to Section 10.0 Safety). V0 should take place 2 days (+12 days) after Independent Rater Screening is completed. Visit 0 and Visit 1 may take place on the same day.

## 7.2 Preparatory Period with Enrollment Confirmation

Participants will undergo three Preparatory Sessions (Visits 1, 2, and 4) lasting approximately 90 minutes with the therapy team prior to the first Experimental Session. The Preparatory Period will be initiated within 12 days of Visit 0 and last 2-11 weeks, depending on duration of medication tapering. There must be at least 48 hours between Preparatory Sessions. The minimum time to complete the Preparatory Period is 2 weeks. The Preparatory Period will also include the Baseline CAPS-5 assessment (Visit 3), which will be assessed by an IR.

Adherence criteria for Preparatory Sessions should be followed per the Treatment Manual. In these visits, the therapy team will work with the participant to prepare for MDMA-assisted psychotherapy, begin building therapeutic alliance, and promote a safe set and setting for confronting trauma-related memories, emotions, and thoughts.

## 7.2.1 Preparatory Session 1 and Preparatory Session 2

Preparatory Sessions during the Preparatory Period will focus on psychoeducation about PTSD, building safety for the therapeutic relationship, developing the therapeutic alliance, obtaining the background for the trauma, and preparing the participant for the first Experimental Session. Telephone calls may be scheduled between visits if indicated for tapering, safety, or any further questions about medical history.

- Preparatory Session 1 (Visit 1) will occur within 1 week (0 to 12 days) of Visit 0. The visit timing should take into account appropriate times for monitoring medication tapering.
- Preparatory Session 2 (Visit 2) will occur within 3 weeks of Visit 0 and at least 2 days after Visit 1. The visit timing should take into account appropriate times for monitoring medication tapering. Visit 2 must take place at least 2 days after and within 3 weeks of Preparatory Session 1 (Visit 1)

• If tapering is ongoing at Preparatory Session 2 (Visit 2), the site team will schedule a telephone call after tapering and stabilization are complete to confirm that the participant is eligible for the Baseline CAPS-5 assessment. If tapering is complete or not needed, the site team will confirm eligibility and schedule Baseline CAPS-5 T1 (Visit 3) and Preparatory Session 3 (Visit 4) as soon as possible.

At each 90-minute psychoeducation and psychotherapy Preparatory Session, the therapy team will:

- Record the therapy session.
- Inquire about any possible changes in health to ensure the participant continues to meet all eligibility requirements. Record AEs as described in Section 10.0 Safety.
- Inquire about concomitant medication use and adherence.
- Confirm that medication tapering is ongoing or complete, as appropriate.
- Discuss goals and expectations for the Experimental Session, following standard procedures and techniques described in the Treatment Manual [111].

If a participant would like a companion present during or after the Experimental Session, a meeting between the therapy team and that individual will be scheduled prior to the first Experimental Session. There must be mutual agreement between the participant and therapy team concerning the presence of the companion and companion should receive study information to read and to sign informed consent form before joining therapy or experimental sessions.

During one of the Preparatory Sessions, if possible, the therapy team will introduce the participant to the attendant who will remain with the participant during each overnight stay after each MDMA-assisted psychotherapy session. The attendant will be an individual with previous training in managing psychological distress. The site will make all attempts to have the same attendant for each Experimental Session for a given participant, but it is not guaranteed.

At any time during the Preparatory Period, if a potential participant is deemed to be ineligible, the site team will classify them as an Enrollment Confirmation Failure, notify the potential participant that they are unfortunately not eligible for the study, and not schedule additional assessments.

#### 7.2.2 Baseline: CAPS-5 by Independent Rater

At Visit 3, an IR will measure the Baseline CAPS-5 (referred to as Baseline CAPS-5 T1) via tele-assessment as soon as possible after medication tapering, stabilization, and two Preparatory Sessions are complete. This visit will be recorded to video to establish inter-rater reliability. The scores will be sent as soon as possible to the site staff. A CAPS-5 Total Severity Score of at least 35 is required to meet Enrollment Confirmation criteria. The IR will also administer the DSP-I and SDS.

#### 7.2.3 Baseline: Preparatory Session 3 and Enrollment Confirmation

Prior to Visit 4, the site team will review the results of the IR visit to ensure that the CAPS-5 Total Severity Score is at least 35. Visit 4 should be scheduled within 6 days of the Baseline CAPS-5 assessment but ideally will take place as close to Experimental Session 1 (Visit 5) as possible, but not on the same day.

At Visit 4, the site team will confirm eligibility by reassessing specified eligibility criteria and ensuring that the participant continues to agree to all lifestyle modifications. If the participant continues to be eligible for the study, enrollment will be confirmed (after approval from the Medical Monitor for the initial participants until confidence is established). If any requirements are not met before or during Visit 4, the participant will be considered a Pre-Dosing Early Termination.

For eligible participants at Visit 4, qualified site staff will ensure at least 3 hours are scheduled for the visit and:

- Collect urine sample for pregnancy test from PABP.
- Perform urine drug test.
- Perform alcohol test (UK only).
- Administer Since Last Visit C-SSRS to determine suicidal risk.
- Actively support participant in the completion of Baseline self-reported measures:
  - o PCL-5- ensure assessment is in relation to index trauma
  - o ACE
  - o BDI-II
  - o CPGS
  - o EQ-5D-5L
  - o SCS
  - o SRNU
  - o EAT-26
  - o UFEC and economic productivity

Completion of the measures does not need to be recorded.

- Complete the third 90-minute Preparatory Session (as described in Section 7.2.1 Preparatory Sessions 1 and 2) with the purpose of confirming all enrollment is met and completing final preparation for the first Experimental Session.
- Remind the participants of lifestyle modifications, including fasting and refraining from using psychoactive or non-approved medications, pertinent prior to the Experimental Session per Section 3.3 Lifestyle Modifications.
- Schedule Visit 5.

#### 7.3 Treatment Period

During the Treatment Period, which occurs over a duration of 5 to 12 weeks (Visits 5 to 13), participants will complete two treatments. Each treatment consists of an Experimental Session, followed the morning after by an Integrative Session, phone follow-ups over the next week, a second Integrative Session within 2 weeks, and a third Integrative Session within 3 to 5 weeks. The Experimental Sessions will be scheduled 3 to 5 weeks apart. The CAPS-5 will be assessed at one time point during the Treatment Period: CAPS-5 T2 after Integrative Session 1.2 (Visit 7). The Primary Outcome CAPS-5 T3 will be assessed after the last Experimental Session during the Follow-up Period.

## 7.3.1 Experimental Sessions

## 7.3.1.1 Psychotherapy Session

There will be two open-label Experimental Sessions (Visits 5 and 10). Procedures for MDMA-assisted psychotherapy will remain the same across all sessions and all procedures regardless of dose received (Table 7). Experimental Sessions must be at least 8 hours long, measured from 30 minutes prior to IP administration.

- Experimental Session 1 (Visit 5) will occur within 1 week of the Baseline CAPS-5 (Visit 3) assessment. If the Baseline CAPS-5 assessment is completed outside of the allowed window, the investigator should consult the CRA and Medical Monitor to determine if the assessment should be repeated. The first Experimental Session will include 80 mg of IP followed by a supplemental half-dose 1.5 to 2 hours after the initial dose unless tolerability issues emerge with the first dose or the participant declines.
- Experimental Session 2 (Visit 10) will occur within 3 to 5 weeks of Experimental Session 1 (Visit 5) and after Integrative Session 1.3 (Visit 9). A dose of 80 or 120 mg MDMA will be administered. A supplemental half-dose will be administered 1.5 to 2 hours after the initial dose unless tolerability issues emerge with the first dose or the participant declines.

Table 8: Schedule of Procedures for Experimental Sessio
--

Approximate Time	Procedure or Action
9:30	Urine drug screen, alcohol test (UK only), pregnancy test, Symptom-
	directed Physical Exam, concomitant medication information collected,
	participant acclimated to environment, C-SSRS
9:55	Baseline BP, body temperature, pulse, SE
10:00	IP Administration, Begin video recording
11:30	BP, body temperature pulse, SE
	Supplemental Dose Administration, unless tolerability issues emerge
	with the first dose or the participant declines
17:30	C-SSRS, BP, body temperature, pulse, SE

#### Pre-IP administration

- On the day of the Experimental Session, the participant will arrive approximately 30 to 60 minutes prior to IP administration.
- The site team will ensure the participant has not used caffeine or nicotine 2 hours prior and fasted for 10 hours prior to IP administration and complied with all other requirements per Section 3.3 Lifestyle Modifications.
- The site team will inquire about any possible changes in health to ensure the participant continues to meet all eligibility requirements and record AEs as described in Section 10.0 Safety.
- The site team will instruct the participant that they will not be able to use caffeine or nicotine at least 6 hours after the IP administration.
- The site team will complete symptom-directed physical exam, urine drug screen, pregnancy test, and concomitant medication review.
  - a. A positive drug screen will be reviewed by the site physician and may be cause for delaying IP administration to a later time, rescheduling the session to a later date, or withdrawing the participant from the study, based on Medical Monitor review.

- b. A positive pregnancy screen is cause for withdrawal from the protocol.
- The therapy team will administer Since Last Visit C-SSRS.
- The therapy team will review procedures for the Experimental Session with the participant and discuss the participant's goals, intentions, and concerns and some of the commonly experienced effects of MDMA. The choice of whether to keep the dose the same or change it from the first Experimental Session will be made by the therapy team in consultation with the site physician based on observed response, tolerability to the previously administered dose, and discussion with the participant.
- If the participant continues to be eligible, the session will proceed.
- Baseline blood pressure, body temperature, and pulse will be measured just prior to administration of the initial dose. Participant subjective effects (SE) self-rated VAS measures on 15 items (negative mood, body perception changes, confusion, difficulty concentrating, compassion for self, compassion for others, euphoria, positive mood, intellectual efficiency, social, calmness, talkative, open to new experiences, meaningful experience, emotional distress) will be collected at three time points: prior to initial dose of MDMA, prior to supplemental dose of MDMA and at the end of the experimental session (see Table 8). A symptom-directed physical examination will be conducted at any time if clinically indicated.

## During the Experimental Session

- After video recording has begun, at approximately 10:00 in the morning, a qualified staff member will administer the initial dose of IP with water. The participant will sit or recline on comfortable furnishings. Eyeshades and a program of music will be provided for the participant if they wish to use them. Whenever they wish, participants may speak to the therapy team, who will provide guidance and support, as needed.
- After the first hour, if the participant has not spoken spontaneously, the therapy team will check in with them about the nature of the experience. For the rest of the experience, as appropriate, the therapy team will support and encourage the participant in emotional processing and resolution of whatever psychological material is emerging, as described in the Treatment Manual.
- Fluids will be provided throughout the session but not to exceed three liters overall.
- Blood pressure, body temperature, pulse and SE will be measured approximately 1.5 to 2 hours after the initial dose, before the supplemental dose is administered.
- The site physician (if not part of the therapy team) will be contacted with a brief description of how the session is progressing and the recent vital signs. The site physician will approve or deny the administration of the supplemental dose. If medical attention is needed, the site physician will provide further instruction or consult the Medical Monitor.
- A supplemental half-dose will be administered with a glass of water approximately 1.5 to 2 hours after the initial dose, unless the participant experiences tolerability issues.
- Food will be provided during the latter part of the session.
- If there is an approved companion, that person may arrive as agreed upon but will remain in the waiting room until a member of the therapy team brings them to the session room. Alternatively, the companion may arrive after the session has ended.

### End of Experimental Session

- The therapy team will administer Since Last Visit C-SSRS.
- The therapy team will record AEs and concomitant medications.

- Blood pressure, body temperature, pulse and SE will be measured including a symptomdirected physical exam if clinically indicated.
- The session may be ended if all medical and psychiatric parameters are acceptable, elevations in vital signs have resolved to pre-IP levels, the participant is alert, ambulatory, and emotionally stable, and the night attendant has arrived.
- The therapy team or site physician shall remain available to participants via 24-hour cellular phone for integration, as needed.

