### 1.2.2 MDMA

MDMA is a ring-substituted phenylisopropylamine derivative invented by Merck pharmaceutical company in 1912 [25, 26]. Similar to SSRIs, MDMA binds to the monoamine transporters, with the greatest affinity for the serotonin transport (SERT). MDMA also enhances synaptic levels of serotonin, and to a lesser extent norepinephrine and dopamine, by vesicular carrier-mediated release and reuptake inhibition of these neurotransmitters [27-33]. MDMA increases levels of affiliative neurohormones oxytocin and vasopressin, which is associated with increased trust and attenuation of reactivity to threatening cues, and cortisol and prolactin. The indirect effects of MDMA on central and peripheral neurohormone release contribute to a novel mechanism that may help regulate the HPA axis, which would treat the core psychopathology of PTSD for a durable remission.

Onset of MDMA effects occurs ~0.5 to 1 hour after oral administration, and peak effects occur 1.25 to 2 hours after the initial dose. Effects of the initial dose last 3 to 6 hours, which is extended to 5 to 8 hours with a supplemental half-dose administered 1.5 to 2 hours post initial dose. Orally administered MDMA has a half-life of 7 to 9 hours in humans. Unlike approved PTSD medications, therapeutic effects of MDMA have a rapid onset, and do not require daily dosing or a steady state in the blood to be effective. Thus, the effects of MDMA are distinct from and work through different mechanisms than anxiolytics and SSRIs. Furthermore, there is no evidence that limited doses of MDMA in controlled clinical settings creates a physical dependence or drug seeking behavior. Previous studies of polydrug users have found a small percentage of people exhibit problematic use of Ecstasy (material represented as containing MDMA) [34, 35]. Studies of regular or problematic Ecstasy users indicate that on average, regular use occurs no more often

than once a week [36]. Hence, MDMA is said to have moderate abuse potential in non-medical settings, and low abuse potential in clinical settings. See the Investigator's Brochure (IB) for a more detailed explanation.

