Table 6: Time and Events – Treatment and Follow-up Period

	Treatment Period ~8 weeks (+/-3 weeks)										Follow-up Period & Study Termination (~4 weeks) 13 weeks (+/-3 weeks) post baseline		
			Treatmen	t 1			Treat	Primary	Study				
Visit	V5	V6	V7	V8	V9	V10	V11	V12	V13	Outcome V14	Termination V15		
Visit Description	Exp. 1	Int. 1.1	Int. 1.2	CAPS-5 T2: Tele- assessme nt	Int. 1.3	Exp. 2	Int. 2.1	Int. 2.2	Int. 2.3	CAPS-5 T3 Outcome: Tele- assessment A	Study Termination		
Visit Timing	Within 1 week of V3	Mornin g after V5	3 to 14 days after V5	18 to 30 days after V5	20 to 34 days after V5	21 to 35 days after V5	Morning after V10	3 to 14 days after V10	20 to 34 days after V10	13 weeks post V5 (+/-3 weeks)	2 days post V14 (-1/+7 days)		
Concomitant medication review	✓	✓	✓		✓	✓	✓	✓	✓		✓		
Symptom-directed Physical Exam	√					√					√B		
Drug Test C	✓					✓							
Pregnancy Test D	✓					✓			✓				
Digital Recording of Visit	✓	✓	✓	✓	✓	✓	✓	✓	✓	✓			
AE Assessment E	✓	✓	✓		✓	✓	✓	✓	✓		✓		
Administer IP	✓					✓							
8-hour Exp. Session	✓					✓							
Blood Pressure, Pulse, Temperature F	✓					✓					✓		
Overnight Stay	✓					✓							
90-min Integrative Session		✓	✓		✓		✓	✓	✓				
Phone Call Follow-up G	1.1.1.	✓	1 0		DG 5 FD		✓ /	11 . 1	:1.1.12	1 (1/2 1)	175		

A All visits must be scheduled to ensure that the Primary Outcome CAPS-5 T3 assessment is within the overall window provided: 13 weeks (+/-3 weeks) post V5

B At Study Termination, includes weight. A symptom-directed physical exam to be conducted only if clinically indicated.

<sup>C In the UK, also includes testing for alcohol. Must be completed prior to IMP dosing.

<sup>D PABP only. At Visit 5 and Visit 10, a negative urine pregnancy test must be confirmed prior to IMP dosing.

<sup>E Adverse Events (Aes) Assessment includes collecting Serious Adverse Events, Aes of Special Interest, Aes of Psychiatric Status, Aes requiring medical advice or attention, Aes that indicate withdrawal of a participant, and all other Aes.

F During Experimental Sessions, vitals are measured before Investigational Product administration, immediately before the supplemental dose is administered (or would be, if supplemental dose not given), approximately 8 hours after initial dose, and as needed.

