3.3 Safety Objectives

The overall safety objective is to assess severity, incidence and frequency of AEs, AEs of Special Interest (AESIs), and Serious Adverse Events (SAEs), concomitant medication use, suicidal ideation and behavior, and vital signs to support the package insert for MDMA-assisted psychotherapy. The following safety objectives will evaluate the safety of MDMA-assisted psychotherapy:

- 1. Assess incidence of AEs during Experimental Sessions that may be indicative of a medical complication of the Investigational Product (IP), such as clinical signs and symptoms of chest pain, shortness of breath, or neurological symptoms or any other signs or symptoms that prompt additional vital sign measurements.
- 2. Assess incidence of AEs by severity.
- 3. Assess incidence of Treatment Emergent AEs (TEAEs) by severity.
- 4. Assess incidence of TEAEs by severity taken during an Experimental Session and through 2 days after IP administration.
- 5. Assess incidence of AESIs, defined as AEs specified in he protocol related to cardiac function and abuse liability.
- 6. Assess incidence of AEs by severity categorized as leading to discontinuation of IP, resulting in death or hospitalization, and continuing at Study Termination.
- 7. Assess incidence of SAEs.
- 8. Assessincidence of psychiatric concomitant medications taken during an Experimental Session and through 2 days after IP administration.
- 9. Assess incidence of any psychiatric concomitant medications taken during the Treatment Period.
- 10. Assess incidence of serious suicidal ideation and positive suicidal behavior assessed with the Columbia Suicide Severity Rating Scale (C-SSRS).
- 11. Assess mean changes in blood pressure, heart rate, and body temperature from pre-IP administration to end of each Experimental Session.

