8.8.5 Summary of Vital Signs

Vital signs (heart rate, BP, and body temperature) for Experimental Sessions will be summarized using descriptive statistics in tabular format listing values at pre-IP, prior to the supplemental dose, and at the end of each Experimental Session.

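### Safety objective 11 measures vital-sign change at a time when the acute rise is expected to be gone; the planned tables hold mid-session values but no paired change to them and no maximum

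*Protocol*

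**What the plan says.** Objective 11, in Protocol 2.3 and SAP 3.3, reads: "Assess mean changes in blood pressure, heart rate, and body temperature from pre-IP administration to end of each Experimental Session". The overall safety objective above it says that these data, vital signs included, are to support the package insert.

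The Protocol section on the end of the Experimental Session lists a set of vital-sign measurements and then the release rule, one condition of which is that "elevations in vital signs have resolved to pre-IP levels". No tolerance around the pre-dose level is given, and the rule concerns elevations only.

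Two places time the last reading. Table 8 puts it at 17:30 ("C-SSRS, BP, body temperature, pulse, SE") after dosing at 10:00. Table 6, note F, puts it at "approximately 8 hours after initial dose, and as needed".

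A mid-session reading is taken 1.5 to 2 hours after the initial dose, before the supplement. By Table 6, note F, it is also taken when no supplement is given. Protocol 1.2.2 says that "peak effects occur 1.25 to 2 hours after the initial dose".

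For analysis, SAP 8.8.5 plans descriptive statistics "listing values at pre-IP, prior to the supplemental dose, and at the end of each Experimental Session", and Protocol 13.1.2 says the same. Neither defines a change score or a maximum.

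**The concern.** The second anchor of the change score is the point at which the protocol requires any rise to have gone. Where the rule is followed, a participant with a large acute rise and one with a small rise can give the same end-of-session change. A small mean change would then be evidence of recovery, yet under objective 11 as worded it could be reported as the size of the vital-sign effect.

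This matters for a package insert. Protocol 9.2.2.1 describes a dose-dependent rise in blood pressure and says that its characterisation in controlled hypertension is still under way; such participants may enrol here (inclusion criterion 11). For earlier studies, Protocol 9.2.3.1 reports temperature as peak above baseline, which is the kind of summary that objective 11 leaves out.

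**Working it through.** The documents state no vital-sign effect and no sample-size calculation, so there is no figure to reproduce. The check sets the timings side by side, derives a bound and adds an illustration.

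**Timings, in hours after the initial dose**

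- Peak effects: 1.25 to 2 (Protocol 1.2.2).
- Mid-session reading: 1.5 to 2 (Protocol 7.3.1.1); in Table 8, 11:30 − 10:00 = 1.5.
- Earliest session end: "Experimental Sessions must be at least 8 hours long, measured from 30 minutes prior to IP administration", so 8 − 0.5 = 7.5.
- Last scheduled reading: 17:30 − 10:00 = 7.5 (Table 8), or about 8 (Table 6, note F).
- Expected duration of heart-rate and blood-pressure changes: at most 8 (Protocol 9.2.2.1).
- Stretch with no scheduled reading: from 7.5 − 2 = 5.5 to 8 − 1.5 = 6.5 hours.

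The mid-session reading lies inside the stated peak window. The last reading lies at or close to the stated upper limit on duration.

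**Bound if the release reading is analysed.** Let P be the pre-dose value, E the reading on which the session is ended and t any tolerance that sites apply. The rule gives E ≤ P + t, so each change E − P ≤ t, and the mean change is ≤ t whatever the peak was. Taken literally, t = 0. Readings below P are not constrained, so the mean is at or below zero.

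**If the first clock-timed reading is analysed.** The bound does not apply. The expectation of a value near baseline then rests on the duration statement in Protocol 9.2.2.1, which covers heart rate and blood pressure but not temperature.

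**Illustration; every input is assumed.** Mean peak rise is 10, 20 or 30 mmHg, with a between-person SD of one third of the mean. The rise falls linearly from 2 hours to zero at a time uniform between 5 and 9 hours, with no second rise after the supplement. Reading SD is 5 or 8 mmHg and release tolerance 0 or 5 mmHg. The first end reading is at 7.5 hours, repeated every 30 minutes for up to 4 hours until release; 89% to 98% are released in that time. Ranges run over the four SD and tolerance combinations.

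| Assumed mean peak (mmHg) | Change to mid-session reading | Change to fixed 7.5 h reading | Change to release reading |
|---|---|---|---|
| 10 | 10.0 | 0.4 to 0.5 | −7.5 to −1.9 |
| 20 | 20.0 | 0.8 to 0.9 | −7.4 to −1.8 |
| 30 | 29.9 to 30.0 | 1.3 | −7.3 to −1.6 |

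Tripling the peak moves the fixed-time change by 0.8 to 0.9 mmHg and the release change by 0.1 to 0.3 mmHg. The mid-session change moves by about 20, but that column equals the peak by construction: the model places the mid-session reading at the peak. The informative columns are the last two. The negative release values arise because release selects readings that happen to be low relative to the pre-dose value.

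**What the planned table gives.** With complete pairs, the mean change to mid-session is the difference of two tabulated means. The spread of individual changes is not recoverable: SD² = s₁² + s₂² − 2·r·s₁·s₂, and the correlation r is not tabulated. With s₁ = s₂ = s, the SD of the change could lie anywhere from 0 (r = 1) to √2·s ≈ 1.41·s (r = 0). The largest individual rise cannot be recovered either. Extra readings prompted by symptoms fall outside the three tabulated times, and SAP 8.0 sends data not subject to planned analysis to listings only.

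**The case against.** A reader might infer that the study will report no acute vital-sign effect, or that the endpoint is zero by design. The documents support neither.

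First, the mid-session values are planned output. Protocol 13.1.2 and SAP 8.8.5 tabulate them for each session, so the mean acute rise can be read off by subtraction. This stands. The defect lies in the objective's contrast and in missing summaries; the data are collected.

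Second, the strict bound needs the analysed end reading to be the one that releases the participant. The protocol lists the measurement before the release rule, both schedules are timed from the dose, and nothing says that a raised value is replaced by a later one. This also stands: the documents leave open which reading counts. Eight hours is moreover an upper limit, Protocol 1.2.2 gives effects of 5 to 8 hours with the supplement, and a reading at 7.5 hours may carry some residual rise.

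Third, objective 11 could be read as covering changes over the whole session. That fits the three-point table, but it leaves the objective without a defined summary of the acute change, so the gap remains.

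Fourth, the peak window in Protocol 1.2.2 refers to effects of the initial dose in general, and the mid-session reading precedes the supplement. Protocol 4.5 says only that the supplement should not produce physiological effects much above the initial peak. A later, higher value is possible and the mid-session reading would miss it. A maximum that includes unscheduled readings depends on how often each person is measured. Both limits stand and shape the fix.

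Finally, this is an open-label lead-in of up to 40 participants, and the sponsor already has pooled data showing a dose-dependent rise. That lowers the stakes without making the stated contrast informative.

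**Conclusion.** The point holds in a limited form. The change score in objective 11 is expected to be at or near zero, and at or below zero if the release reading is used without tolerance, so it does not reflect the acute rise. This rests on sites following the release rule or, for a clock-timed reading, on the protocol's own statement of how long heart-rate and blood-pressure changes last. The documents give no effect size; in the assumed scenarios, a 20 mmHg difference in peak shifts the end-of-session change by less than 1 mmHg.

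The mean acute rise remains obtainable from the planned table. What is missing is the paired change with its spread, any maximum, any tabulation of unscheduled readings, and a definition of the end reading. This is an inexpensive improvement to make before the analysis and does not call the conduct of the study into question.

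**What to change.** In objective 11 and SAP 8.8.5:

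1. Add, as the acute-effect summary, the paired change from pre-dose to the pre-supplement reading (n, mean, SD, median, range), by session and initial dose. The dose split is descriptive only, because the session 2 dose is chosen partly on tolerability.
2. Report separately each participant's highest recorded value and its change from pre-dose. Flag unscheduled readings and state that the maximum depends on how often readings were taken.
3. Keep the end-of-session value as a recovery measure, and state whether the first clock-timed reading or the release reading is analysed when measurement is repeated.
4. Reconcile the 7.5-hour timing in Table 8 with the timing of about 8 hours in Table 6, note F, and its SAP counterpart.

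The session-ending rule is not touched and no new scheduled measurement is needed. The cost is one extra table and the wording. The remaining weakness is that the pre-supplement reading may miss a later peak; only the flagged unscheduled readings bear on that interval.
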